#### 13.3.3 Pharmacokinetic population

The PK population will include patients from the all-treated population with at least 1 drug concentration after the first dose of study treatment.

## 13.3.4 Pharmacodynamic population

The pharmacodynamic population will include patients from the all-treated population with at least 1 pharmacodynamic marker result after the first dose of study treatment.

#### 13.3.5 Anti-drug antibody evaluable population

ADA evaluable population will include all patients from the all-treated population with at least 1 ADA non-missing result after the first dose of study treatment.

#### 13.3.6 Cross-over population

The cross-over population is defined as patients in Cohort A-2 who progressed on isatuximab monotherapy and received isatuximab in combination with REGN2810.

## 13.3.7 Response evaluable population

The response evaluable population will include all patients in the all-treated population who fulfill all eligibility criteria with an evaluable baseline assessment and at least one evaluable post-baseline response assessment during the treatment period.

#### 13.4 STATISTICAL METHODS

A list of study endpoints and their definitions are provided in Section 9.6.

Unless otherwise specified, analyses will be descriptive and performed based on the all-treated population. The baseline for a given parameter is defined as the last assessment for this parameter before first administration of study treatments unless otherwise noted.

Data from mCRPC and NSCLC cohorts in the Phase 2 part will be analyzed and reported separately by cohort. Data from the cohort A-2 cross-over part will be summarized separately unless otherwise noted.

Continuous data will be summarized using number of available data, mean, standard deviation, median, minimum and maximum for each dose level (if applicable). Categorical and ordinal data will be summarized using number and percentage of patients in each dose level (if applicable). Summary tables will be presented by dose level and overall (if applicable), unless otherwise noted.

## 13.4.1 Demographics and baseline characteristics

Demographic and baseline characteristics (including age, gender, race, ECOG performance status), medical or surgical history, and disease characteristics at diagnosis and at study entry will be summarized using descriptive statistics.

## 13.4.2 Extent of investigational medicinal product exposure

The following variables will be described to summarize the overall study treatment exposure (all study treatments together):

- Overall number of cycles started.
- Duration of overall exposure in weeks.

In addition, the following variables will be summarized with descriptive statistics for each IMP (ie, isatuximab and REGN2810):

- Number of cycles started with each drug.
- Duration of exposure of each drug in weeks.
- Number of infusions.
- Cumulative dose.
- Actual dose intensity.
- Relative dose intensity.
- Dose reduction and reason for dose reduction.
- Cycle delays.
- Infusion delays within a cycle.
- Infusion interruption.
- Dose omission.

#### 13.4.3 Prior/concomitant medication/therapy

Prior and concomitant medications will be summarized according to the World Health Organization Drug Dictionary, considering the first digit of the Anatomical Therapeutic Chemical (ATC) class (anatomic category) and the first 3 digits of the ATC class (therapeutic category). All ATC codes corresponding to a medication will be summarized. Patients will be counted once in each ATC categories (anatomic or therapeutic) linked to the medication.

#### 13.4.4 Analyses of efficacy variables

All efficacy analyses will be performed using the all-treated/safety population unless otherwise specified. More details on efficacy analyses including the analyses for exploratory endpoints will be provided in the SAP.

## 13.4.4.1 Analysis of primary efficacy endpoint

The RR will be summarized using descriptive statistics. A 90% 2-sided confidence interval will be computed using Clopper-Pearson method. The statistical inference will be based on the hypothesis defined in Section 13.1 using a 1-sided exact binomial test with a significance level of 0.05 for each cohort. For each cohort, the analysis cut-off date for the primary analysis of RR will be 6 months after the last patient's first treatment in the cohort. The analysis cut-off date for secondary efficacy endpoints including DoR and PFS will be 12 months after the last participant's first treatment in the cohort. The primary analysis of RR will be updated.

Same analysis will be performed for RR using the response evaluable population as a secondary analysis. Subgroup analyses for primary endpoint may be performed if relevant.

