#### Phase 2 part

The Phase 2 part of the study is to evaluate initial anti-tumor activity based on tumor response using RECIST 1.1 criteria for NSCLC and PCWG3 criteria for mCRPC. The efficacy evaluation is based on Simon's 2-stage design with 90% power at 5% 1-sided alpha level for each of the patient cohorts of mCRPC and NSCLC patients respectively.

The assumption of RR, the required sample sizes, and the number of responders at each stage are provided below:

Indication	H₀	H 1	Sample size		Number (%) of responses to reject H		
			Stage 1	Final	Stage 1	Final	
mCRPC (Combo)	10%	26%	23	49	≥3 (13.0%)	≥9 (18.4%)	
mCRPC (Single)	10%	26%	23	49	≥3 (13.0%)	≥9 (18.4%)	
NSCLC (Combo)	5%	22%	20	36	≥2 (10.0%)	≥5 (13.9%)	

Abbreviations: H₀=null hypothesis; H₁=alternative hypothesis; mCRPC=metastatic, castration-resistant prostate cancer; NSCLC=non-small cell lung cancer.

Note: Based on the number of objective responses and the totality of data observed within a treatment cohort in Phase 2 Stage 1, the Sponsor may decide to advance such a treatment cohort to Phase 2 Stage 2 after consulting with Investigators.

Patients who received the RP2D in Phase 1 will be also included in Phase 2 Stage 1 (eg, if 6 NSCLC patients were enrolled in Phase 1, only 14 NSCLC patients will be needed to complete the Phase 2 Stage 1 NSCLC cohort).

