### 6.3 PHASE 2 PART (EFFICACY SIGNAL)

The Phase 2 part may include up to 5 cohorts (see design diagram in Section 1.1):

- Cohort A-1: mCRPC, isatuximab and REGN2810 combination therapy.
- Cohort A-2: mCRPC, isatuximab monotherapy.
- Cohort B: NSCLC, isatuximab and REGN2810 combination therapy.

- **Possibly Cohort C**: mCRPC, isatuximab and REGN2810 combination therapy, or isatuximab monotherapy without initial isatuximab weekly dosing.
- **Possibly Cohort D**: NSCLC, isatuximab and REGN2810 combination therapy without initial isatuximab weekly dosing.

A Simon's 2-stage design will be used in each cohort. Enrollment in Cohort A-2 will start only if the decision to proceed to Phase 2 Stage 2 in Cohort A-1 is made.

The patients treated at the RP2D of isatuximab and REGN2810 in combination during Phase 1 will be included in the efficacy analysis together with patients of the same tumor type in Stage 1 of Phase 2. Based on the number of objective responses (observed at least 6 cycles after the last ongoing patient receives first dose of IMP) and the totality of data observed within a treatment cohort in Phase 2 Stage 1, the Sponsor may decide to advance such a treatment cohort to Phase 2 Stage 2 after consulting with Investigators. After enrollment completion of Phase 2 Stage 1, if efficacy results do not warrant initiation of Stage 2, enrolment will be paused until sufficient results or analyses warrant initiation of Phase 2 Stage 2.

For patients with mCRPC, if it is decided to run Phase 2 Stage 2, an isatuximab monotherapy cohort will be initiated for this population (Cohort A-2); patients with mCRPC will be randomly assigned in a 1:1 randomization ratio to enter Cohort A-1, isatuximab and REGN2810 combination (Phase 2 Stage 2) or Cohort A-2, isatuximab monotherapy (Phase 2 Stage 1). The isatuximab single agent dose and schedule for cohort A-2 is 10 mg/kg QW for 3 weeks followed by Q3W.

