#### 13.1 DETERMINATION OF SAMPLE SIZE

## Phase 1

In Phase 1, approximately 6 (assuming 6 patients for the starting dose) to 24 (assuming 12 patients for the starting dose plus 12 patients for DL-1) DLT evaluable patients are expected to be enrolled. The actual sample size will vary depending on DLTs observed and the number of dose levels explored. Patients who are not evaluable for DLT assessment in the Phase 1 part may be replaced.

#### Phase 2

The Phase 2 part of the study is to evaluate initial anti-tumor activity based on tumor response using RECIST 1.1 criteria for NSCLC and PCWG3 for mCRPC. The efficacy evaluation is based on Simon's 2 stage design with 90% power at 5% 1-sided alpha level for each of the patient cohorts of mCRPC and NSCLC patients, respectively. The assumption of RR, the required sample sizes and the number of responders at each stage are provided in Table 8.

Indication Нο Н₁ Sample size Number (%) of responses to reject Ho Stage 1 **Final** Stage 1 **Final** mCRPC (Combo) 23 49 10% 26%  $\geq 3 (13.0\%)$  $\geq 9 (18.4\%)$ mCRPC (Single) 10% 26% 23 49  $\geq 3 (13.0\%)$  $\geq 9 (18.4\%)$ ≥2 (10.0%) NSCLC (Combo) 5% 22% 20 36  $\geq$ 5 (13.9%)

Table 8 - Sample size calculation

Abbreviations:  $H_0$ =null hypothesis;  $H_1$ =alternative hypothesis; mCRPC=metastatic, castration-resistant prostate cancer; NSCLC=non-small cell lung cancer.

Note: Based on the number of objective responses and the totality of data observed within a treatment cohort in Phase 2 Stage 1, the Sponsor may decide to advance such a treatment cohort to Phase 2 Stage 2 after consulting with Investigators.

Patients who received the recommended dose regimen in Phase 1 will be also included in the Phase 2 Stage 1 (eg, if 6 NSCLC patients were enrolled in Phase 1, only 14 NSCLC patients will be needed to complete the Phase 2 Stage 1 NSCLC cohort).

In Phase 2, approximately 134 patients are expected to be enrolled (assuming Cohort A-1, A-2 and B complete 2 stages), including approximately 66 patients in Phase 2 Stage 1 and approximately 68 patients in Phase 2 Stage 2. The patients who are treated with RP2D in the Phase 1 part will be counted as Phase 2 part patients. If isatuximab 10 mg/kg Q3W in combination

11-Jun-2019 Version number: 1

with REGN2810 or monotherapy without the isatuximab 10 mg/kg QW for 3 weeks is to be tested in a mCRPC or NSCLC cohort, 49 or 36 additional patients will be needed, respectively.

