2.4.5.1 Analysis of primary efficacy endpoint(s)

The RR will be summarized using descriptive statistics. A 90% 2-sided confidence interval will be computed using Clopper-Pearson method. BOR will be summarized descriptively. For mCRPC cohorts, PSA response will also be summarized using descriptive statistics.

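### In the mCRPC cohorts, 9 responses in 49 reject H0 by the Simon boundary but not by the exact binomial test or Clopper-Pearson interval the protocol specifies

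*Protocol*

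**What the plan says.** Protocol 13.1 (Table 8, repeated in the Clinical Trial Summary) sizes each cohort by "Simon's 2 stage design with 90% power at 5% 1-sided alpha level for each of the patient cohorts". For mCRPC, combination and single agent alike, H0 is 10% and H1 is 26%. Stage 1 has 23 patients and needs at least 3 responses; the final sample is 49 and needs at least 9. The column holding those counts is headed "Number (%) of responses to reject Ho".

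Protocol 13.4.4.1 refers the primary inference to the Section 13.1 hypothesis, "using a 1-sided exact binomial test with a significance level of 0.05 for each cohort", and adds a 90% 2-sided Clopper-Pearson interval. It does not mention the two stages.

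On Stage 1, Protocol 6.3 says that, given the number of responses and the totality of data, "the Sponsor may decide to advance such a treatment cohort to Phase 2 Stage 2 after consulting with Investigators".

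SAP 2.4.5.1 keeps the interval ("A 90% 2-sided confidence interval will be computed using Clopper-Pearson method") and names no test. SAP 1.3 repeats the Simon design with its power and alpha. SAP 1.5 declares no change to the protocol's statistical section.

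**The concern.** A Simon boundary and an ordinary exact binomial test are different rules. The Simon boundary takes credit for trials that would have stopped at Stage 1, which removes some of the null probability of reaching 9. An ordinary exact test on 49 patients takes no such credit, and neither does a Clopper-Pearson interval. For the mCRPC design the two approaches fall on opposite sides of 5% at exactly the boundary count.

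A cohort finishing with 9 responses would therefore be a success by Table 8 and a failure by the specified p-value and interval, and no text says which prevails. This is the primary efficacy conclusion for Cohorts A-1 and A-2, and for C if it opens. Opening C depends in turn on positive results in A-1 or A-2. If the choice is left until the data are in, whoever chooses the rule chooses the result.

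**Working it through.** **Inputs (Protocol Table 8 and 13.4.4.1).** p0 = 0.10, p1 = 0.26, n1 = 23, r1 = 3, n = 49 (so n2 = 26), r = 9. Test: exact binomial, 1-sided, 0.05. Interval: Clopper-Pearson, 90% 2-sided.

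**Step 1. Reproduce the stated design.** The probability of rejecting under the two-stage rule is

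R(p; r) = Σ over x1 = 3,…,23 of P(X1 = x1 | 23, p) × P(X2 ≥ r − x1 | 26, p).

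- R(0.10; 9) = 0.0479
- R(0.26; 9) = 0.9015

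The stated 5% alpha and 90% power both reproduce, so Table 8 is correct for a two-stage rule.

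**Step 2. Apply the test and interval in 13.4.4.1.**

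- Exact p-value: P(X ≥ x | 49, 0.10).
- Clopper-Pearson limits: the 0.05 quantile of Beta(x, 50 − x) and the 0.95 quantile of Beta(x + 1, 49 − x).

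| Responses | Exact p | 90% Clopper-Pearson | Excludes 10%? |
|---|---|---|---|
| 9/49 | 0.0519 | 9.93% to 29.86% | No |
| 10/49 | 0.0215 | 11.51% to 32.15% | Yes |

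The smallest count that rejects under the specified test is 10, not 9.

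**Step 3. Power of the test as written (10 or more of 49).**

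- With the Stage 1 stop: R(0.26; 10) = 0.8425 and R(0.10; 10) = 0.0205.
- Without the stop: P(X ≥ 10 | 49, 0.26) = 0.8553, with alpha 0.0215.

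The loss against the design's own power is 0.9015 − 0.8425 = 0.0590 with the stop in force.

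**Step 4. How often the conflict occurs.** The probability of passing Stage 1 and ending on exactly 9 is R(p; 9) − R(p; 10).

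- Under H1: 0.9015 − 0.8425 = 0.0590, or 5.9%
- Under H0: 0.0479 − 0.0205 = 0.0274 from the rounded figures (0.0273 unrounded), or 2.7%

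**Step 5. Dependence of alpha on the Stage 1 stop.** For 9 or more of 49 at p = 0.10:

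- Stop enforced at 2 or fewer of 23: 0.0479
- Cohort advanced with 2/23, still stopped at 0 or 1: 0.0511
- Stop never enforced: 0.0519

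**Step 6. Interval matched to the design.** Solving R(p; 9) = 0.05 gives p = 0.1008. The two-stage lower limit at 9/49 is therefore 10.08%, which excludes 10% and agrees with Table 8.

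**Step 7. NSCLC for comparison.** H0 is 5% and the final boundary is 5/36. The exact p is 0.0324 and the interval is 5.64% to 27.01%. Test, interval and boundary agree.

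**The case against.** The best counter-argument is that 13.4.4.1 points back to Section 13.1, which specifies a Simon design, and that Simon's rule is itself an exact binomial calculation. Read that way, 9/49 governs, its p-value is 0.0479, and the stated alpha and power hold. The interval could then be treated as description, since no passage makes success depend on its lower limit. This reading is possible, but the text does not state it, and an exact binomial test ordinarily means the single-stage test. The Clopper-Pearson limit of 9.93% would also still sit beside a declared rejection of 10%.

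Several points limit the weight of the finding, and they stand:

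- Only one outcome, exactly 9 responses, is affected.
- The alpha excess without a binding stop is at most 0.19 percentage points (5.19% against 5%). Protocol 6.3 also says enrolment will be paused if Stage 1 efficacy does not warrant continuing, and discretion to stop a cohort that met 3/23 would lower alpha.
- The power shortfall is smaller (85.5%) if the Stage 1 stop is ignored.
- The study is a non-comparative signal search, and its decisions also weigh the totality of data.
- Within the SAP alone there is no contradictory p-value, because no test is named.

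These bear on how serious the defect is. They do not remove it.

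**Conclusion.** The point holds: the plan is wrong as written for the mCRPC cohorts. Table 8 is sound as a two-stage rule, but the test and interval in Protocol 13.4.4.1 do not reproduce its boundary. At 9/49 the plan gives opposite answers (two-stage alpha 0.0479, single-stage p = 0.0519), and under the test as written power is 84.3% with the Stage 1 stop, or 85.5% without it, against the stated 90%. The p-value conflict and the power figures assume the ordinary single-stage meaning of an exact binomial test. The mismatch between the interval and the boundary does not depend on that assumption. The SAP leaves the matter open, because the interval is its only inferential output for the primary endpoint.

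**What to change.** Choose one rule and write it into Protocol 13.4.4.1 and SAP 2.4.5.1 before any mCRPC cohort is analysed.

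1. **Preferred: let the Simon boundary govern.** Reject H0 if there are at least 3/23 and then at least 9/49. Report the two-stage exact p-value and a two-stage interval (for example Koyama-Chen or Jung-Kim). State that the 5% alpha assumes a binding Stage 1 stop, and give 5.2% as the figure if it is not enforced. If the Clopper-Pearson interval is kept as well, label it descriptive and say that it does not decide the outcome.
2. **Alternative: keep the exact binomial test and Clopper-Pearson interval.** Change the mCRPC final threshold to at least 10/49 and restate the power as about 84%.

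Under either option, name the test in the SAP and record any departure from the protocol in SAP 1.5. The cost is wording and a few lines of code. Sample size and data collection do not change. The second option also means publishing a less favourable power figure.

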## 13.4.4.2 Analysis of secondary efficacy endpoints

The following secondary endpoints will be analyzed:

- Tumor burden change: the best percent-change from baseline in tumor burden will be summarized and presented graphically for patients with measurable disease at baseline. In addition, a summary of the AUC and the time-adjusted AUC of percent-change from baseline in tumor burden will also be provided as an exploratory analysis.
- Duration of response: Kaplan-Meier estimates such as median and Kaplan-Meier curves will be provided for patients who achieved a response.
- Progression-free survival: the PFS will be analyzed using the Kaplan-Meier method. The Kaplan-Meier estimates of the 25th, 50th and 75th percentiles and the 95% confidence intervals of median will also be computed. The Kaplan-Meier curves will be plotted.
- Disease control rate: the DCR will be summarized using descriptive statistics.

Subgroup analyses for secondary endpoints may be performed if relevant.

#### 13.4.5 Analyses of safety data

## 13.4.5.1 Dose-limiting toxicities

In the Phase 1 part, the DLTs will be listed by patient using the DLT evaluable population.

## 13.4.5.2 Analyses of adverse events

The observation period will be divided into 3 segments: pretreatment, TEAE and posttreatment:

- The pretreatment period is defined as the time informed consent is signed until the first dose of study treatments administration.
- The TEAE period is defined as the time from the first dose of study treatments up to 30 days after last dose of study treatments.

11-Jun-2019 Version number: 1

• The posttreatment period is defined as the time starting 31 days after the last dose of study treatments to study closure or death, whichever comes first.

Pretreatment AEs are defined as any AE during the pretreatment period.

Treatment-emergent AEs are defined as AEs that develop, worsen (according to the Investigator opinion) or become serious during the TEAE period.

Posttreatment AEs are defined as AEs that are reported during the posttreatment period.

The grade will be taken into account in the summary. For patients with multiple occurrences of the same PT, the maximum grade will be used.

The primary focus of AE reporting will be on TEAEs. Pretreatment and posttreatment AEs will be described separately.

## Treatment-emergent adverse events

The TEAEs will be coded according to MedDRA. The AEs will be graded according to the NCI-CTCAE version 4.03.

An overall summary of TEAEs will be provided. The number and percentage of patients who experience any of the following will be provided:

- TEAEs.
- TEAEs of >Grade 3.
- Grade 5 TEAE (any TEAE with a fatal outcome during the treatment period).
- Serious TEAEs.
- Serious treatment-related TEAEs.
- TEAE leading to permanent (full study treatment) discontinuation/premature (partial study treatment) discontinuation.
- AESIs.
- Treatment-related TEAEs.
- Treatment-related TEAEs of > Grade 3.

The number and percentage of patients experiencing TEAEs by primary SOC and PT will be summarized by NCI CTCAE grade (all grades and ≥Grade 3). Similar tables will be prepared for treatment-related TEAEs, AESIs, TEAEs leading to permanent/premature discontinuation, TEAEs leading to dose modification, serious TEAEs, TEAEs with fatal outcome and AEs/SAEs occurring during the posttreatment dosing period.

Sorting within tables should ensure the same presentation for the set of all AEs within the observation period (pretreatment, on-treatment and posttreatment). For that purpose, the table of all TEAEs will be presented by SOC and PT sorted by internationally agreed order unless otherwise specified.

#### 13.4.5.3 Deaths

The following deaths summaries will be generated:

- Number (%) of patients who died by study period (TEAE and posttreatment) and reasons for death summarized for the all-treated/safety population.
- TEAEs with fatal outcome (on the AE e-CRF page as reported by the Investigator), and related TEAEs with fatal outcome summarized by primary SOC and PT.

A listing of deaths will be provided.

#### 13.4.5.4 Clinical laboratory evaluations

Clinical laboratory values will be analyzed after conversion into standard international units. International units will be used in all listings and tables. Complete blood count and serum chemistry results will be graded according to NCI-CTCAE version 4.03, when applicable. For patients with multiple occurrences of the same laboratory variable during the TEAE period, the maximum grade (worst) per patient will be used. The denominator used for percentage calculation is the number of patients with at least 1 evaluation of the laboratory test during the considered observation period.

The number and proportion of patients with abnormal laboratory tests at baseline (ie, last assessment before the first dose of study treatments administration) will be presented for all grades together and each grade separately. Similar tables showing abnormalities during the TEAE period will be provided.

When the NCI-CTCAE version 4.03 scale is not applicable, the number of patients with a laboratory abnormality out-of-normal laboratory range value will be displayed.

## 13.4.5.5 Vital signs

Potentially clinically significant abnormality (PCSA) values are defined as abnormal values considered medically important by the Sponsor according to predefined criteria/thresholds based on literature review. The incidence of PCSA during the TEAE period will be summarized.

## 13.4.5.6 Immunogenicity

The observation period for ADAs will be divided into 2 periods:

- The ADA pretreatment period will be defined as the time that informed consent is signed until the first study treatment administration.
- The ADA on-study observation period will be defined as the time from the first study treatment administration until the end of the study.

